### **3.0 RESPONSIBILITIES OF THE PRINCIPAL/ASSOCIATE INVESTIGATOR IN HUMAN SUBJECTS RESEARCH:**

IRBNet Number: 381600-19

PI: [name]

Protocol Title: **A randomized, single-blind, prospective trial of auricular acupuncture for the reduction of post-operative tonsillectomy pain in adults.**

Initial Date Submitted: 6/13/2013

Revision Date: 7/17/17

The principal investigator is the individual who is primarily responsible for the actual execution of the clinical investigation. He/she is responsible for the conduct of the study, obtaining subjects' consent, providing necessary reports, and maintaining study documents. The Associate Investigator will assist the Principal Investigator with the responsibilities stated below.

As the Principal Investigator or Associate Investigator:

**A.** I will not enroll a subject into a study until the study has been approved by the appropriate authority and, when appropriate, the subject's primary care provider has granted approval for him/her to enter a study.

**B.** By signing this protocol, I warrant that any use of Protected Health Information (PHI) for reviews preparatory to research met the following requirements:

- i. The review of PHI was done solely to prepare a research protocol, or for similar purposes preparatory to research;
- ii. No PHI was taken outside the Military Health Care System or disclosed to persons not having a need for this information; and
- iii. This review of PHI was necessary for research purposes

**C.** I am responsible for assuring that the prospective volunteer is not participating as a subject in other research that will significantly increase the research risks to the subject.

**D.** I am responsible for assuring the quality of each subject's consent in accordance with current federal regulations. This will include ensuring that any "designee" that obtains consent on my behalf is completely conversant with the protocol and is qualified to perform this responsibility.

**E.** I will obtain the WAMC IRB approval for advertisements used to recruit research subjects.

**F.** I will not accept any outside personal remuneration for implementation of a study.

**G.** I will take all necessary precautions to ensure that the study does not generate hazardous chemical waste.

**H.** I will obtain the proper WAMC clearance prior to all presentations, abstracts, and publications. The following require WAMC approval:

- i. Reports involving WAMC subjects and/or patients.
- ii. Reports that cite WAMC in the title or byline.
- iii. Reports of WAMC approved clinical investigation or research.
- iv. Reports of research performed at WAMC.
- v. Reports of research conducted by WAMC assigned personnel.

**I.** I will obtain proper Office of the Surgeon General (OTSG) publication clearance prior to all presentations, abstracts, and publications that involve:

IRBNet Number: 381600-19

PI: [name]

Protocol Title: **A randomized, single-blind, prospective trial of auricular acupuncture for the reduction of post-operative tonsillectomy pain in adults.**

Initial Date Submitted: 6/13/2013

Revision Date: 7/17/17

- i. Traumatic brain injury
- ii. Post-traumatic stress disorder
- iii. Poly-pharmacy
- iv. Pain

(Contact [name] at [[contact]](mailto:[contact]) for assistance.)

**J. I must submit to the Clinical Investigation Service (CIS):**

- i. Any source of outside funding.
- ii. An annual Continuing Review Report (CR), due in the anniversary month of the protocol's initial approval or due in the month as determined by the IRB for continuing review and approval.
- iii. Reports of adverse effects occurring in subjects as a result of study participation or of any protocol deviations and submit these reports to Research Monitor if there is one for the study.
- iv. An Addendum, prior to any changes made to the study or a change in the funding status.
- v. Listing of presentations, abstracts, and publications arising from the study for inclusion in the CR.

**K. I will maintain a Study File that must be kept for six years following completion of the study if no IND/IDE used (32 CFR 219.115(b)). If IND medication or IDE appliances are used, the file must be kept for 2 years after FDA approval and can then be destroyed; or if no application is filed or approved, until 2 years after the study is discontinued and FDA notified (21CFR 312.62(c)). The records should be kept in the Department/Service where the research took place (AR 40-38). If I am scheduled to PCS or ETS, I will notify the Clinical Investigation Service as soon as I am aware but at least 3 months prior to departure. Records will be given to a new WAMC PI or the Department/Service Chief.**

**L. I will be familiar with all applicable regulations governing research, and will adhere to all of the requirements outlined in the WAMC's DOD Assurance and Federal-Wide Assurance granted by the Office for Human Research Protections, Department of Health and Human Services.**

**M. Research Monitor**

If it is determined that a Research Monitor is assigned to the research study, I agree to provide the name, human subject protection training and curriculum vitae of the research monitor. I acknowledge that this individual will be qualified (e.g., Medical Doctor, Nurse Practitioner, etc). The research monitor will review all unanticipated problems involving risk to the subjects or others, serious adverse events and all subject deaths associated with the protocol and provide an unbiased written report of the event. At a minimum, the research monitor will comment on the outcomes of the event or problem, and in the case of a serious adverse event or death, comment on the relationship to participation in the study. The research monitor will also indicate whether he/she concurs with the details of the report provided by the study investigator. Reports for events determined by either the investigator or research monitor to be possibly or definitely

IRBNet Number: 381600-19

PI: [name]

Protocol Title: **A randomized, single-blind, prospective trial of auricular acupuncture for the reduction of post-operative tonsillectomy pain in adults.**

Initial Date Submitted: 6/13/2013

Revision Date: 7/17/17

related to participation and reports of events resulting in death will be promptly forward to the WAMC IRB.

#### **N. Active Duty Military Personnel as Study Subjects**

Special consideration will be given to the recruitment process for military personnel. The Chain of Command will not be involved in the recruitment of military personnel and will not encourage or order soldiers to participate in research study. An ombudsman will be used when conducting group briefings with active duty personnel to ensure that volunteers understand that participation is voluntary. Restrictions on compensation for active duty military members will be adhered to as applicable.

#### **O. Title 10 United States Code 980**

I acknowledge the requirements of Title 10 United States Code 980: "Funds appropriated to the Department of Defense may not be used for research involving a human being as an experimental subject unless-(1) the informed consent of the subject is obtained in advance; or (2) in the case of research intended to be beneficial to the subject, the informed consent may be obtained from a legal representative of the subject."

If an individual cannot give his or her own consent (e.g., incapacitated individuals, incompetents, minors) to participate in the research study, consent of the individual's legally authorized representative will be obtained prior to the individual's participation in the research. Moreover, such subjects will not be enrolled in DoD sponsored research unless the research is intended to benefit each subject enrolled in the study.

**4.0 LOCATION OF STUDY:** Womack Army Medical Center

**5.0 DURATION OF STUDY:**

**Expected Start Date for Data Collection: July 2013**

**Expected Completion Date for Data Collection: July 2017**

**Expected Completion Date for Study (to include data analysis): January 2018**

**6.0 BACKGROUND AND LITERATURE REVIEW:**

**Date of Search: 01 April 2013**

**Period Searched: 1970s-present**

**Sources Searched: Pubmed; OVID**

**Keywords Searched: acupuncture; tonsillectomy; auricular acupuncture; battlefield acupuncture**

IRBNet Number: 381600-19

PI: [name]

Protocol Title: **A randomized, single-blind, prospective trial of auricular acupuncture for the reduction of post-operative tonsillectomy pain in adults.**

Initial Date Submitted: 6/13/2013

Revision Date: 7/17/17

Tonsillectomy is one of the most commonly performed surgical procedures in the United States. While the procedure is more commonly performed in pediatric patients, greater than 130,000 were performed for patients older than 15 years in 1996. Indications for tonsillectomy in adults primarily include recurrent tonsillitis, soft tissue obstruction, and neoplasm. Several variations of surgical technique are available, each having a different impact on post-surgical bleeding and pain. These most commonly include cold dissection, electrosurgery, harmonic scalpel, laser dissection, guillotine tonsillectomy, argon plasma coagulation, and coblation. Each of these methods possesses its advantages and disadvantages, and the decision on which to use typically rests on the surgeon's own preference and training. However, all of these techniques result in significant post-operative pain, with this found to be worse in adults. Patients experience a high level of pain usually for the first four days after surgery, and pain can persist for up to ten days. Opioids are the most commonly prescribed analgesics for post-operative pain in adults.

Opioids, steroids, and non-steroidal anti-inflammatory agents have all been utilized in the attempt to minimize pain. Although shown to be effective in controlling post-operative pain, the use of narcotics comes with unpleasant side effects such as nausea, vomiting, and constipation. As dehydration is a common complication after a tonsillectomy due to limited swallowing capability, the side effects of narcotics can further exacerbate this problem. Other commonly used treatments for pain include non-steroidal anti-inflammatory drugs (NSAIDs) and acetaminophen. Both have been found to be effective in controlling post-operative pain, but should be used with caution. Due to their antiplatelet effect, NSAIDs in particular can be harmful after tonsillectomy, as bleeding is a common morbidity with this surgery. Acetaminophen has little impact on clotting; however, long-term usage or over dosage can result in liver failure. Steroids (typically dexamethasone) are used to prevent inflammation, but may also have some analgesic benefit. While no adverse effects have been shown, efficacy studies have produced mixed results, with some reporting an improvement in pain post-operatively and others reporting no effect observed. Another alternative treatment for post-operative pain is a local anesthetic administered either by infiltration or applied topically. While moderately improving pain after surgery, this method was not found to reduce the use of supplemental analgesia. As demonstrated, pharmacotherapy has its benefits and its risks. As such, alternate methods for controlling post-operative pain should be considered.

Acupuncture is an ancient Chinese method of treating pain in which needles are inserted into zones on the body that correspond to certain body parts. Although used in traditional Chinese medicine for centuries, acupuncture as an alternative method of treating pain in the Western world has been a topic of increased clinical studies over the past few decades, as it is relatively low-risk and cost-effective. A literature review of studies dating back to the 1970s indicated that a vast majority of the data pointed to the efficacy of acupuncture in treating neck and back pain, dental pain, musculoskeletal and arthritic pain, as well as chronic pain. A more recent meta-analysis demonstrated further mounting evidence of the analgesic effects of acupuncture on a wide variety of pain, including osteoarthritis and migraines. Its potential in post-operative analgesia has also been studied, and acupuncture has been shown to reduce pain as well as decrease the use of opioids after a number of various surgeries. Although a few

IRBNet Number: 381600-19

PI: [name]

Protocol Title: **A randomized, single-blind, prospective trial of auricular acupuncture for the reduction of post-operative tonsillectomy pain in adults.**

Initial Date Submitted: 6/13/2013

Revision Date: 7/17/17

studies have given inconclusive results, there is an overwhelming amount of promising data to suggest that acupuncture may play an important role in analgesia.

Many different acupuncture techniques are commonly used for managing pain; specifically, auricular acupuncture has been a long-standing therapeutic modality dating back thousands of years. The use of auricular acupuncture has been applied to many conditions including headache, allergic rhinitis, chronic fatigue, anxiety and pain. The hypothesized efficacy of auricular acupuncture comes from the premise that the external ear represents a microsystem of the entire body. The ear serves as a miniature homunculus, whereby specific points on the ear correspond to specific areas of the body. A modified technique, referred to as Battlefield Acupuncture (BA), was developed by [name] in 2001 and utilizes only five major auricular points (see Figure 1). [name] collaborated with a neurophysiologist to determine which areas of the brain were activated in patients experiencing pain. They utilized functional MRI to visualize these pain centers and found less activity in these areas after the application of auricular acupuncture. BA is an appealing method of analgesia since it can be easily taught, easily applied, does not require highly specialized equipment or sterile operating conditions, and is inexpensive. Furthermore, its risks are minimal, including irritation or possible infection of the ear. To our knowledge, this is the first single-blinded, prospective, randomized trial evaluating the efficacy of BA in reducing post-operative pain for adult tonsillectomy.

PI: [name]

Protocol Title: **A randomized, single-blind, prospective trial of auricular acupuncture for the reduction of post-operative tonsillectomy pain in adults.**

Initial Date Submitted: 6/13/2013

Revision Date: 7/17/17

report of pain according to the Numerical Rating Scale (NRS) (0= no pain, 10 = worst imaginable pain) up to 10 days post-operation.

**7.1 HYPOTHESES/RESEARCH QUESTIONS:** We hypothesize that subjects receiving intra-operative auricular acupuncture during a tonsillectomy will have statistically significantly less post-operative pain scores in comparison to subjects receiving standard of care.

## **7.2 SPECIFIC AIMS/SIGNIFICANCE:**

**Aims:** The specific aim of this study is to compare post-operative pain, as measured by Sum of Pain Intensity (SPI) from the time of first to waking to 10 days post-operative using the Numerical Rating Scale (NRS), between subjects receiving intra-operative auricular acupuncture or standard of care during a tonsillectomy.

**Significance:** Post-operative pain in adults after a tonsillectomy is significant, despite surgical technique and medication management. Identification of an intra-operative intervention that results in significant reduction in post-operative pain would improve patient's quality of life, and may reduce medication usage and improve return-to-duty time.

**Secondary aims:** We will also compare outpatient pain medication use and resumption of normal diet between subjects receiving intra-operative auricular acupuncture or standard of care during a tonsillectomy.

## **7.3 DESIGN:**

- **Design type: Prospective, randomized control trial**
- **Sample**
  - **Description of the population:** All adults (>18 years) undergoing a tonsillectomy with or without adenoidectomy at WAMC are eligible for participation in the study.
  - **Sample Size: 125 subjects.** A target of 45 subjects per group for a total of 90 subjects, and accounting for a 10% drop out rate. With current diary return low, to ensure complete data for analysis we will continue to recruit and enroll up to 125 subjects.
  - **Power Analysis:** Under the assumption of a linear time by treatment interaction, assuming subject-level randomization, five time-points, power of 80%, a Type I error rate of 5% and no attrition, to detect a 1.6 difference in pain score requires a total sample size of 90 subjects or 45 per treatment arm.
  - **Inclusion Criteria:**
    - All adults (males and females) 18 yrs of age or older having a tonsillectomy or tonsillectomy with adenoidectomy.
    - ASA I-III
  - **Exclusion Criteria:**
    - Chronic pain syndromes (pain symptoms lasting greater than three months or taking opioids on a daily basis for > 3 months)
    - ASA IV

IRBNet Number: 381600-19

PI: [name]

Protocol Title: **A randomized, single-blind, prospective trial of auricular acupuncture for the reduction of post-operative tonsillectomy pain in adults.**

Initial Date Submitted: 6/13/2013

Revision Date: 7/17/17

- Prior neck or throat surgery
- Allergy to gold

- **Number of Participants:** Up to 125 subjects will be enrolled with a target of 90 subjects (45 per group) that have completed the study. .

- **Explanation of the process from consenting to data collection:**

- **Randomization:** Before the study begins, a randomized, sequential set of 100 numbered opaque envelopes will be prepared containing assignment to either the acupuncture group or the control group. The randomization list will be generated by a computer program. The envelopes will be stored in the PIs office and opened according to subject number on the day of surgery. To continue enrollment up to 125 another 25 will be randomized using a computer randomization program.

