- If screening criteria based on inclusion and exclusion criteria are not met the potential participant will be thanked for their time and informed that they do not qualify for the study.
- If the patient meets the screening criteria and verbalizes interest in participating in the study, he or she is notified that s/he can be scheduled to further review and complete the consent paperwork if s/he wishes with study staff when s/he is present for the pre-admission appointment or at another time convenient for the potential participant. Then, at that time, the potential participant will have a chance to review any questions s/he may have about the study and complete the study consent paperwork if s/he wishes to participate. Consenting will take place in advance of the day of the procedure; if possible and if not a team member will meet with potential participant on the day of surgery in holding. Once a subject has consented to be in the study, the individual consenting them will interview them for demographics, medical history, medication history, and allergies (Appendix A). The pain diary will be reviewed at this time as well. If the subject is determined to be eligible for the study, her/his scheduled date of surgery will be confirmed. The PI will keep a list of all subjects and their respective surgery dates in a password protected electronic enrollment log kept in the V drive.
- **Home diary teaching:** At the Pre admit and/or consent appointment, a research team member will review the home pain diary with the subject. They will be asked to record their pain score in 6 hour intervals for 24 hours after hospital discharge and every 24 hours for a total of 10 days after the surgery. Subjects will not be asked to wake up at night to record pain level. Subjects will be asked to return their pain scores by phone, email, or mail (addressed envelope provided). If the subject has not sent their diary by day 15, an attempt at a reminder to the subject via phone call or email (whichever the subject prefers, as collected during enrollment) will be done. .
- **On the day of the surgery:** On the day of surgery, the randomization category will be determined by the PI or AI acupuncturists by opening the corresponding subject number envelope. Prior to surgery, the PI or AI acupuncturists will introduce him or herself to the subject (if not already done so) and confirm enrollment in the study. Anesthesia for the surgical case will then proceed per standard of care.

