**Data collection:** Data will be collected and entered into three forms (Appendices A-C). All forms will be maintained in a locked file cabinet in the PI's locked office. Data will be collected during the initial subject interview by the individual consenting them (Appendix A), on the day of surgery by the PI (Appendix B), and from the home pain diary. (Appendix C). Data on the day of surgery may also be collected from Essentris or the anesthesia record once the patient has been discharged (as all data needed will be recorded in Essentris or the anesthesia record). Data will be transferred from these forms to an electronic Data base. Each patient will be allocated a study ID number, and thereafter will be referred to by that number in the database. An Excel spreadsheet with all current data will be where the data is to be entered by a research team member. It will be maintained in the V drive with limited password access. Only research team members will have access.

- Total doses of opioid analgesics in the preoperative, intraoperative and postoperative period will be converted to IV morphine equivalents by the PI or research staff member. They will use John Hopkins Opioid Program's conversion at <http://www.hopweb.org/hop/hop.cfm>
- **Acupuncture Competence:** The PI completed the 300 CME Helms Medical Acupuncture Course, the DOD wide approved acupuncture course.

• **Data Collection Instrument:**

- **Appendix A: Data collection form for demographic and contact information to be collected after initial consent prior to surgery**
- **Appendix B: Data form for day of surgery data collection**
- **Appendix C: The home diary to be completed by the subject**

• **Other Appendices**

- **Appendix D: Flow chart of recruitment to discharge**
- **Appendix E : Screening inclusion/exclusion**
- **Appendix F: Script for MSA's (Medical Support Assistants)**

IRBNet Number: 381600-19

PI: [name]

Protocol Title: **A randomized, single-blind, prospective trial of auricular acupuncture for the reduction of post-operative tonsillectomy pain in adults.**

Initial Date Submitted: 6/13/2013

Revision Date: 7/17/17

- **Appendix G: Optional Research Packet (flyer/information sheet/envelope)**
- **Appendix H: Data Excel**

• **Variables/Data Points:**

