**Figure 2. Table of Variables/Data Points**

Variable	Data Source
Age	Patient report
Race	Patient report
Gender	Patient report
Height and Weight	Essentris or Ahlta
Pain scores	Patient report and Essentris
Pre op and PACU pain scores	Essentris
Total time in OR	Essentris
Surgical date	Patient report, confirmed in S3
Total OR time	Essentris
Needle retention time	Documented by the PI
Type of Surgery	Essentris
Needle type	Documented by the PI
Intraoperative anesthetic	Essentris
Dexamethasone dose	Essentris
Total Morphine Equivalent	Essentris and John Hopkins Converstion
Daily pain scores	Home diary
Post op Nausea/Vomiting	Essentris notes
Day diet returned to normal	Home diary
Oral pain meds at home	Home diary

**7.4 RISKS TO SUBJECTS:** Acupuncture is considered a safe technique with minimal risk to the subject. Acupuncture needles only penetrate the skin approximately one millimeter. Despite the minimal penetratruion, needle insertion poses the risk of infection, bleeding and bruising. All acupuncture needles used in this study will be sterile and inserted after alcohol preparation of the ear surface. The needles are made of gold and pose minimal, if any, allergic reaction.

IRBNet Number: 381600-19

PI: [name]

Protocol Title: **A randomized, single-blind, prospective trial of auricular acupuncture for the reduction of post-operative tonsillectomy pain in adults.**

Initial Date Submitted: 6/13/2013

Revision Date: 7/17/17

**8.0 DATA ANALYSIS:** The primary metric for this study is pain score. Pain scores will be collected for 10 days post-operatively, as previous studies have demonstrated a return to baseline by this time. Pain scores will be collected daily during this time period, resulting in repeated measures for each subject. Analysis will be conducted by mixed models to evaluate both (1) difference in pain scores by groups and (2) rate of change in pain score over time.

Age and sex will be considered as potential confounders. Duration of needle insertion may also be evaluated for effect on outcome, if significant variability in length is noted. The type of surgical technique (cold knife coblation versus cautery) may be a potential confounder. Finally, intra-operative anesthesia and dexamethasone dose will be evaluated for potential confounding.

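### The pre-operative pain score is collected but not named as a covariate in the pain analysis, which gives up some precision in the comparison of pain level

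*Combined protocol and SAP*

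**What the plan says.** **Eligibility (section 7.3).** Entry is open to "All adults (males and females) 18 yrs of age or older having a tonsillectomy or tonsillectomy with adenoidectomy", ASA I-III. The pain-related exclusion is "Chronic pain syndromes (pain symptoms lasting greater than three months or taking opioids on a daily basis for > 3 months"). The other exclusions are ASA IV, "Prior neck or throat surgery" and gold allergy; none concerns current pain or current opioid use. Subjects with pain or daily opioid use of three months or less are therefore eligible.

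**Data collected.** Figure 2 includes "Pre op and PACU pain scores", taken from Essentris. At consent, study staff "will interview them for demographics, medical history, medication history, and allergies (Appendix A"). Under data collection in section 7.3, "Total doses of opioid analgesics in the preoperative, intraoperative and postoperative period will be converted to IV morphine equivalents".

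**Analysis.** Section 8.0 plans mixed models for two things: the difference in pain scores between groups, and the rate of change over time. On covariates it says "Age and sex will be considered as potential confounders", then adds needle duration (if it varies enough), surgical technique, intra-operative anesthesia and dexamethasone dose. Figure 3 gives study group as the only predictor and starts the pain outcome after surgery. The pre-operative score is thus neither a listed covariate nor a time point in the model. Home morphine equivalents are compared by Student's t-test on study group alone. Section 7.2 states the aim as the Sum of Pain Intensity (SPI) from first waking to day 10.

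**The concern.** The baseline value of an outcome is often among its better predictors, and here the trial already records it. The plan itself treats pre-existing pain and opioid use as relevant, since it excludes the long-standing forms. The background section notes that "Indications for tonsillectomy in adults primarily include recurrent tonsillitis, soft tissue obstruction, and neoplasm", so some throat pain before surgery is plausible. Yet the covariate list leaves out pre-operative pain, while including items such as needle duration that take their value after treatment has begun.

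What is at stake is efficiency in a trial of 45 per arm. Any variation in post-operative pain that pre-operative pain could explain stays in the residual. A chance difference between arms in pre-operative pain also passes into the estimated difference in pain level without correction. The same reasoning applies to pre-operative opioid use and the unadjusted comparison of home morphine equivalents.

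**Working it through.** **1. The plan's own figures.** Section 7.3 gives 45 per arm, a 1.6-point difference, 80% power, 5% type I error, five time points and a linear time-by-treatment interaction. It states no SD, within-subject correlation or sidedness, so 90 can be neither reproduced nor refuted. The dropout step does reproduce: 90 / (1 - 0.10) = 100, the number of envelopes first prepared.

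**2. The SD that 45 per arm would imply (assumption: two-sided test).**
- Level comparison: SD = 1.6 / [(1.960 + 0.842) × √(2/45)] = 1.6 / (2.802 × 0.2108) = 2.71.
- Slope test, with five equally spaced times (sum of squares 10), compound symmetry and a 1.6-point difference at the last time (slope difference 1.6/4 = 0.4): SD = √[45 × 10 × 0.4² / (2 × 2.802² × (1 - ρ))]. This gives 2.14, 2.56, 3.03 or 3.91 for ρ = 0, 0.3, 0.5 or 0.7.

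The documents do not say which applies. SD 2.71 is used below only to express the level comparison in NRS points.

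**3. Gain from adjusting the level comparison.** If pre- and post-operative pain correlate at r, adjustment multiplies the residual SD by √(1 - r²). Power = Φ(2.802/√(1 - r²) - 1.960). The unadjusted 95% half-width is 1.96 × 2.71 × 0.2108 = 1.12.

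| r (assumed) | Residual variance removed (r²) | Power | n per arm for 80% | 95% half-width |
|---|---|---|---|---|
| 0 | 0% | 80.0% | 45 | 1.12 |
| 0.2 | 4% | 81.6% | 44 | 1.10 |
| 0.3 | 9% | 83.6% | 41 | 1.07 |
| 0.5 | 25% | 89.9% | 34 | 0.97 |

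**4. Chance imbalance.** A 1.96-SE imbalance in pre-operative pain shifts the unadjusted difference by 1.96 × r × 2.71 × 0.2108 = 0.22, 0.34 or 0.56 points for r = 0.2, 0.3 or 0.5. This is a component of the 1.12 and does not add to it. At r = 0.3, √(0.34² + 1.07²) = 1.12.

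**5. The same check as a subgroup (assumption: 20% of subjects have prior pain or opioid use and score 2 points higher).** The SD of the between-arm difference in their share is √(2 × 0.2 × 0.8 / 45) = 0.084. The 95% range of the shift is 1.96 × 2 × 0.084 = ±0.33 points. The subgroup contributes variance 2² × 0.2 × 0.8 = 0.64 of 2.71² = 7.34, or 8.7%, which corresponds to r = √0.087 ≈ 0.3. Removing it entirely narrows the half-width from 1.12 to 1.96 × √(7.34 - 0.64) × 0.2108 = 1.07 and raises power to about 83.5%.

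**6. The slope test.** A baseline main effect moves all of a subject's scores by the same amount. With balanced data this cancels from the within-subject slope, so the gains in step 3 do not carry over to the time-by-treatment interaction.

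**The case against.** The strongest reply is that the unadjusted analysis is valid. Randomization balances pre-operative pain in expectation, and the standard error and type I error rate already allow for chance imbalance. Adjustment is a matter of efficiency, its size is unknown, and the test used to size the trial hardly benefits. All of this stands, and it limits the point to a precision improvement.

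A reader might infer several stronger things that the documents do not support:

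- **That the three-month limits are a design error.** The wording permits shorter-standing pain or opioid use, but nothing shows that such subjects were enrolled or in what number. The remedy needs no change to the criterion.
- **That nothing balances such subjects because no stratification is described.** Randomization does so in expectation.
- **That ±0.33 points, 21% of the 1.6-point target, is added error.** It is part of ordinary sampling error. Removing it gains about 0.05 points of half-width.
- **That the power gains apply to the 45 per arm as planned.** Section 7.3 powers an interaction, not a level difference.
- **That a yes/no daily-opioid item is ready for use.** Appendix A is not in the supplied text. Section 7.3 mentions only a medication history and a total preoperative opioid dose. Only the pre-operative pain score is clearly available.

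Timing is also a fair objection. The revision is dated 7/17/17, and section 5.0 expected data collection to end in July 2017. The PI or AI acupuncturists open the envelopes, and the PI collects day-of-surgery data. A covariate added now counts as prespecified only if it is fixed before outcomes are examined by arm.

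**Conclusion.** The point holds as a modest loss of precision. A baseline measure of the primary outcome is collected and has no stated place in the analysis. There is no bias in expectation and no fault in eligibility. The benefit falls on the comparison of pain level (the first purpose in section 8.0, and the SPI aim in section 7.2). For a comparison otherwise at 80% power, it is worth about 2, 4 or 10 percentage points of power at correlations of 0.2, 0.3 or 0.5.

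These figures rest on assumed correlations, a two-sided test and 45 analysed per arm, and on the pre-operative score being on the same 0-10 scale. If nearly all subjects score 0 before surgery, the gain is close to nil. The change is worth making because it costs so little.

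**What to change.** Leave the exclusion criterion as it is. Before any outcome data are examined by arm, and with the date recorded:

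1. State in section 8.0 and Figure 3 that the pre-operative NRS score is a fixed covariate in the primary mixed model and in any comparison of SPI. Define which recorded score is used, for example the last before anesthesia, because Figure 2 gives its source but not its time.
2. Where the recorded medication history allows pre-operative opioid use to be derived, adjust the home morphine-equivalent comparison for it, replacing the t-test with the equivalent linear model. If it cannot be derived, keep the t-test.
3. State how missing pre-operative scores are handled, by a rule that does not depend on arm.

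The cost is one or two model degrees of freedom, the missing-score rule and a short amendment. The pain covariate needs no new visits, subjects or measurements and can be applied to subjects already enrolled; the opioid covariate depends on what Appendix A recorded.
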